5.2 Rationale for trial design

Based on prior experience from IDegLira trials, the treatment duration of 26 weeks is sufficient to reach a stable HbA_{1c} level and to obtain sufficient data for efficacy and safety evaluation.

The current trial is designed to demonstrate superiority in HbA_{1c} of IDegLira as compared to IDeg in subjects with T2DM. To enable an evaluation of the contribution of the liraglutide component of IDegLira to glycaemic control and secondary endpoints, the maximum dose of IDeg in the IDeg

arm is set to 50 units, i.e. equivalent to the maximum dose of the IDeg component in IDegLira (50 units of IDeg/1.8 mg of liraglutide).

Two types of insulin are allowed pre-trial (basal and pre-mix/combination insulin), since these may reflect different states of disease progression, the randomisation will be stratified with regards to pre-trial insulin therapy (see section [11.2](#)).

The treat-to-target approach is used in both arms and has been chosen in order to ensure optimal titration based on pre-breakfast SMBG values and thereby to obtain improved HbA_{1c} results.

5.3 Treatment of subjects

Subjects with T2DM treated with 20 to 50 units of basal insulin or pre-mix/combination insulin given once or twice daily in combination with metformin with or without one other OAD are eligible for the trial. Apart from metformin, all other OADs will be discontinued at randomisation. Moreover, basal insulin or pre-mix/combination insulin will be discontinued at randomisation in favour of either IDegLira or IDeg. No other anti-diabetic treatment, or treatment which in the investigators opinion could interfere with weight, glucose or lipid metabolism should be initiated between screening and ET.

Hence, IDegLira and IDeg will be given as add-on to metformin therapy. The trial drugs will be double-blinded and should be injected subcutaneously once daily in the thigh, upper arm (deltoid region) or abdomen. Dosing can be done at any time of the day independent of meals, but should be approximately at the same time of the day throughout the trial for the individual subject. The injection area chosen should remain unchanged throughout the trial, although rotation within the area is recommended. Both trial drugs will be provided in a prefilled device. Titration should be performed twice weekly for both treatment arms (see [Appendix A](#)).

5.3.1 Insulin degludec/liraglutide

The recommended start dose of IDegLira is 10 dose steps (10 units IDeg/0.36 mg liraglutide), with the option of choosing up to 16 dose steps (16 units IDeg/0.6 mg liraglutide) at the investigator's discretion. The 0.36 mg of liraglutide contained in the recommended starting dose almost corresponds to the approved starting dose (0.3 mg) of Victoza[®] in Japan. IDegLira will be titrated twice weekly according to a predefined titration algorithm to a maximum of 50 dose steps (50 units insulin degludec/1.8 mg liraglutide) aiming to reach a FPG target between 4.0 mmol/L (72 mg/dL) and 5.0 mmol/L (90 mg/dL).

5.3.2 Insulin degludec

The recommended starting dose of IDeg is 10 units, with the option of choosing up to 16 units at the investigator's discretion. IDeg will be titrated twice weekly according to a predefined titration

algorithm with a maximum dose of 50 units of IDeg aiming to reach a FPG target between 4.0 mmol/L (72 mg/dL) and 5.0 mmol/L (90 mg/dL).

5.4 Treatment after discontinuation of trial product

When discontinuing trial products, either at the scheduled ET visit or if a subject is withdrawn, the subject should be recommended a suitable marketed product at the discretion of the investigator.

5.5 Rationale for treatment

IDegLira will be investigated to demonstrate efficacy and safety, when administered to insulin experienced subjects with T2DM, inadequately controlled on a stable dose of insulin combined with metformin with or without one other OAD. This is in line with clinical practice to escalate treatment in this setting with the initiation of a GLP-1 receptor agonist, basal insulin or a combination of basal insulin and a GLP-1 receptor agonist, such as IDegLira.

Pre-trial insulin and OAD treatment should be in accordance with current Japanese approved labelling. Subjects should be on at least 90 days of stable treatment (insulin and OADs) defined as unchanged medication and unchanged dose. To reduce the risk of hypoglycaemia all other OADs apart from metformin will be discontinued at randomisation. After randomisation metformin treatment should remain unchanged during the trial, however in case of safety concerns the dose may be reduced at the discretion of the investigator. To avoid impact on trial objectives, no other treatments affecting weight, glucose or lipid should be used, and certain drugs should not be used before the trial (see exclusion criteria no. 5, 6 and 7).

IDeg capped at a maximum dose of 50 units per day have been included as comparator in order to assess the additional effect of the liraglutide component in IDegLira as compared to treatment with IDeg alone at a similar dose.

For further information regarding dosing and treatment refer to [Appendix A](#).

6 Trial population

Number of subjects

Planned number of subjects to be randomised: 210.

Expected number of subjects to complete the trial: 179.

6.1 Inclusion criteria

For an eligible subject, all inclusion criteria must be answered “yes”.

1. Informed consent obtained before any trial-related activities. Trial-related activities are any procedures that are carried out as part of the trial, including activities to determine suitability for the trial.
2. Male or female Japanese subjects ≥ 20 years of age at the time of signed informed consent.
3. Type 2 diabetes mellitus subjects (diagnosed clinically) ≥ 6 months prior to screening.
4. HbA_{1c} 7.5-11.0% [58 mmol/mol-97 mmol/mol] (both inclusive) by central laboratory analysis.
5. Subjects on stable daily insulin doses for at least 90 days prior to screening administered once or twice daily according to current Japanese label, either as basal insulin (e.g. IDeg, insulin glargine, insulin detemir, NPH insulin), or pre-mix/combination insulin (e.g. biphasic insulin aspart, insulin degludec/insulin aspart). Total daily insulin dose in the previous 90 days should be within 20-50 units, both inclusive, and on the day of screening, but fluctuations of $\pm 10\%$ within the 90 days prior to screening are acceptable. The specified insulin treatment should be administered in combination
 - with a stable daily dose of metformin within current approved Japanese label for at least 90 days prior to screening,
 - additionally, the anti-diabetic treatment can be with or without a stable daily dose of one of the following other oral anti-diabetic drugs: sulphonylureas (SU), glinides, α -glucosidase inhibitors (α -GI), sodium-glucose co-transporter-2 inhibitors (SGLT2i) or thiazolidinediones (TZD) within current approved Japanese label for at least 90 days prior to screening.
6. Body Mass Index (BMI) ≥ 23 kg/m².

Rational for inclusion criteria:

- Criterion 1 is applied through an ethical consideration, in accordance with the GCP ¹
- Criterion 2 is applied to exclude minors through an ethical consideration. Subjects aged 65 year or older are included in accordance with the ICH guideline: Studies in support of special populations: Geriatrics¹²
- Criteria 3 and 4 are chosen according to the objective of the trial. Being diagnosed for 6 months or more is required in order to ensure correct diagnosis and metabolic stabilisation. HbA_{1c} range

(7.5-11.0 %) is chosen to include subjects whose glycaemic control is not adequate on pre-trial treatment and intensification is considered possible. The upper limit of HbA_{1c} is chosen in order to exclude subjects with unacceptable glycaemic control who need a more intensive therapy.

- Criterion 5 is applied to ensure that the subject's glycaemic control is stabilised at randomisation. 90 days of unchanged pre-trial treatment are required.
- Criterion 6 is chosen in order to ensure a population allowing for exploring the full dose range of IDegLira, and to minimize the individual impact of any weight loss that may be associated with IDegLira treatment.

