4.2.2 Secondary endpoints

4.2.2.1 Supportive secondary endpoints

Supportive secondary efficacy endpoints:

- Daily insulin dose after 26 weeks
- Change from baseline in body weight after 26 weeks*
- Responder after 26 weeks (yes/no):
 - HbA_{1c} < 7.0%
 - HbA_{1c} < 7.0% and without weight gain
 - HbA_{1c} < 7.0% without treatment emergent severe or BG confirmed symptomatic hypoglycaemic episodes during the last 12 weeks of treatment
 - HbA_{1c} < 7.0% and without weight gain and without treatment emergent severe or BG confirmed symptomatic hypoglycaemic episodes during the last 12 weeks of treatment
 - HbA_{1c} ≤ 6.5%
 - HbA_{1c} ≤ 6.5% and without weight gain
 - HbA_{1c} ≤ 6.5% without treatment emergent severe or BG confirmed symptomatic hypoglycaemic episodes during the last 12 weeks of treatment
 - HbA_{1c} ≤ 6.5% and without weight gain and without treatment emergent severe or BG confirmed symptomatic hypoglycaemic episodes during the last 12 weeks of treatment

- Change from baseline after 26 weeks in:
 - FPG*
 - Waist circumference
 - Blood pressure (systolic and diastolic)
 - Self-measured blood glucose (SMBG) 9-point profile
 - 9-point profile (individual points in the profile)
 - Mean of the 9-point profile
 - Mean of postprandial plasma glucose increments (from before meal to 90 min after breakfast, lunch and dinner). The mean increment over all meals will be derived as the mean of all available meal increments
- Lipid profile after 26 weeks of treatment

Supportive secondary safety endpoints:

- Number of treatment emergent adverse events (TEAE) during 26 weeks of treatment
- Number of treatment emergent severe or BG confirmed hypoglycaemic episodes during 26 weeks of treatment*
- Number of treatment emergent severe or BG confirmed symptomatic hypoglycaemic episodes during 26 weeks of treatment
- Number of treatment emergent hypoglycaemic episodes according to ADA definition during 26 weeks of treatment
- Number of treatment emergent nocturnal severe or BG confirmed symptomatic hypoglycaemic episodes during 26 weeks of treatment
- Change from baseline in clinical evaluation after 26 weeks of treatment:
 - Physical examination
 - Fundoscopy or fundus photography
 - Electrocardiogram (ECG)
 - Pulse
- Change from baseline in laboratory assessments after 26 weeks of treatment:
 - Biochemistry (including amylase and lipase)
 - Haematology
 - Calcitonin

Supportive secondary patient reported outcome endpoints:

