8.7.2 Body Mass Index

BMI will be calculated at screening (V1) for assessment of eligibility (section [6.1](#)).

The BMI will be calculated by the eCRF once body weight and height is entered at screening (V1).

It is calculated as follows:

$$\text{BMI (kg/m}^2\text{)} = \text{body weight (kg)} / (\text{height [m]} \times \text{height [m]})$$

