presented based both on observed and last observation carried forward (LOCF) imputed data. Endpoints that are analysed untransformed and endpoints that are not formally analysed are summarised by the arithmetic mean, standard deviation (SD), median, and minimum and maximum value. Endpoints that are analysed log-transformed are supplemented with the geometric mean and coefficient of variation (CV).

For measurements over time, mean values will be plotted to explore the trajectory over time. LOCF imputed data will be used as the basis for plotting data, if not otherwise specified. For endpoints that are analysed log-transformed, the geometric mean values will be plotted.

A standard analysis of covariance (ANCOVA) model will be applied for the continuous primary and secondary endpoints. The model includes treatment, pre-trial anti-diabetic treatment (metformin + basal insulin, metformin + one other OAD + basal insulin, metformin + pre-mix/combination insulin, metformin + one other OAD + pre-mix/combination insulin) as fixed factors and the corresponding baseline value as covariate. In the following, this model will be referred to as the standard ANCOVA model.

Presentation of results from a statistical analysis will include the estimated mean treatment effects (Least Square Means [LSMeans]) for absolute values and change from baseline. In addition, estimated mean treatment difference (or ratio) will be presented together with the two-sided 95% confidence interval and corresponding two-sided p-value.

Handling of missing data

The expected percentage of missing data is around 15%. In accordance with industry guidance²⁴ endpoints will be assessed at frequent visits. If an assessment has been made both at screening (V1) and randomisation (V2), and if not otherwise specified, the value from the randomisation visit will be used as the baseline value. If the value measured at the randomisation visit is missing and the assessment also has been made at screening, then the screening value will be used as the baseline value.

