17.4 Secondary endpoints

17.4.1 Supportive secondary endpoints

17.4.1.1 Efficacy endpoints

Insulin dose after 26 weeks of treatment

The actual daily dose after 26 weeks of treatment will be analysed using the standard ANCOVA model including treatment and pre-trial anti-diabetic treatment as fixed factors and baseline HbA_{1c} value and baseline insulin dose as covariates.

Responder after 26 weeks of treatment

Two dichotomous endpoints (responder/non-responder) will be defined based on whether a subject has met a specific target level after 26 weeks of treatment:

- HbA_{1c} < 7.0%
- HbA_{1c} ≤ 6.5%

Analysis of each of the two responder endpoints will be based on a logistic regression model with treatment and pre-trial anti-diabetic treatment as fixed factors and baseline HbA_{1c} values as a covariate.

HbA_{1c} responder endpoints without weight gain after 26 weeks of treatment

Responder for HbA_{1c} without weight gain after 26 weeks of treatment will be defined as HbA_{1c} < 7.0% or ≤ 6.5% at ET and change from baseline in body weight bellow or equal to zero. Analysis of each of the two responder endpoints will be based on a logistic regression model with treatment and pre-trial anti-diabetic treatment as fixed factors and baseline HbA_{1c} and baseline body weight values as covariates.

HbA_{1c} responder endpoints without hypoglycaemic episodes

Responder for HbA_{1c} without hypoglycaemic episodes after 26 weeks of treatment will be defined as HbA_{1c} < 7.0% or ≤ 6.5% at ET and without treatment emergent severe or BG confirmed symptomatic hypoglycaemic episodes during the last 12 weeks of treatment. Analysis of each of the two responder endpoints will be based on a logistic regression model with treatment and pre-trial anti-diabetic treatment as fixed factors and baseline HbA_{1c} values as a covariate.

HbA_{1c} responder endpoints without hypoglycaemic episodes and weight gain

Responder for HbA_{1c} without hypoglycaemic episodes and weight gain after 26 weeks of treatment will be defined as HbA_{1c} < 7.0% or ≤ 6.5% at ET, without treatment emergent severe or BG confirmed symptomatic hypoglycaemic episodes during the last 12 weeks of treatment, and change from baseline in body weight bellow or equal to zero. Analysis of each of the two responder endpoints will be based on a logistic regression model with treatment and pre-trial anti-diabetic treatment as fixed factors and baseline HbA_{1c} and body weight values as covariates.

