2.4 Secondary endpoints

2.4.1 Supportive secondary endpoints

2.4.1.1 Efficacy endpoints

Insulin dose after 26 weeks of treatment

The actual daily dose after 26 weeks of treatment will be analysed using the standard ANCOVA model including treatment and pre-trial anti-diabetic treatment as fixed factors and baseline HbA_{1c} value and baseline insulin dose as covariates.

Body weight

The change from baseline in body weight after 26 weeks of treatment will be analysed using the standard ANCOVA model with treatment and pre-trial anti-diabetic treatment as fixed factors and baseline body weight as covariate. Missing values after 26 weeks of treatment will be imputed applying LOCF using body weight values at and after baseline.

Responder after 26 weeks of treatment

Two dichotomous endpoints (responder/non-responder) will be defined based on whether a subject has met a specific target level after 26 weeks of treatment:

- HbA_{1c} < 7.0%
- HbA_{1c} ≤ 6.5%

Analysis of each of the two responder endpoints will be based on a logistic regression model with treatment and pre-trial anti-diabetic treatment as fixed factors and baseline HbA_{1c} values as a covariate.

HbA_{1c} responder endpoints without weight gain after 26 weeks of treatment

Responder for HbA_{1c} without weight gain after 26 weeks of treatment will be defined as HbA_{1c} < 7.0% or ≤ 6.5% at ET and change from baseline in body weight below or equal to zero. Analysis of each of the two responder endpoints will be based on a logistic regression model with treatment and pre-trial anti-diabetic treatment as fixed factors and baseline HbA_{1c} and baseline body weight values as covariates.

HbA_{1c} responder endpoints without hypoglycaemic episodes

Responder for HbA_{1c} without hypoglycaemic episodes after 26 weeks of treatment will be defined as HbA_{1c} < 7.0% or ≤ 6.5% at ET and without treatment emergent severe or BG confirmed symptomatic hypoglycaemic episodes during the last 12 weeks of treatment. Analysis of each of the two responder endpoints will be based on a logistic regression model with treatment and pre-trial anti-diabetic treatment as fixed factors and baseline HbA_{1c} values as a covariate.

HbA_{1c} responder endpoints without hypoglycaemic episodes and weight gain

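### The week-26 insulin dose ANCOVA could include baseline body weight: a near-free change that would probably sharpen a supportive comparison slightly

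*Protocol*

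**What the plan says.** Protocol section 4.2.2.1 lists "Daily insulin dose after 26 weeks" first among the supportive secondary efficacy endpoints, without the asterisk that marks the key ones. Protocol section 17.4.1.1 models it with treatment and pre-trial anti-diabetic treatment as "fixed factors and baseline HbA_{1c} value and baseline insulin dose as covariates". SAP section 2.4.1.1 gives the same model, ending in "value and baseline insulin dose as covariates". Body weight appears in neither.

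A baseline weight is available. The body weight model in SAP section 2.4.1.1 uses "baseline body weight as covariate", and the responder models that involve weight gain adjust for it too. Where a variable is assessed at both V1 and V2, the missing-data text in Protocol section 17 says "the value from the randomisation visit will be used as the baseline value", with screening as the fallback. Weight is certainly taken at screening, since Protocol section 8.7.2 has BMI calculated "once body weight and height is entered at screening (V1").

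The link between body size and dose is in the rationale for inclusion criterion 6, BMI of at least 23 kg/m² (Protocol section 6.1): "Criterion 6 is chosen in order to ensure a population allowing for exploring the full dose range of IDegLira". The same sentence gives a second reason, limiting the impact of weight loss on the individual.

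**The concern.** If the sponsor set a BMI floor partly so that the dose range could be explored, it presumably expects larger subjects to titrate to higher doses. A baseline variable that predicts the outcome and is already in the database would normally be considered as a covariate. The dose model already goes beyond the standard ANCOVA by adding baseline HbA1c, so a tailored covariate list is nothing new here.

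Baseline insulin dose may carry only part of the information in body size. If it means the pre-trial dose, entry restricts it to 20-50 units, it pools basal with pre-mix/combination regimens, and every subject was inadequately controlled on it. If it means the trial-product starting dose (10 to 16 units), it carries less. Neither document defines the term.

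At stake is the width of one confidence interval. That interval bears on the possibility, raised in Protocol section 3.1, that the liraglutide component lowers insulin requirement.

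**Working it through.** **1. The plan's own figures.** The documents give no SD, precision target or power for dose. The only stated power is for HbA1c (Protocol section 17.1). The adjusted difference is 0.85 × 0.45 + 0.15 × 0.20 = 0.4125. With SD 1.0 and 105 per arm, the noncentrality is 0.4125 / √(2/105) = 2.99 on 208 df. The noncentral t power is 84.5%, as stated. Nothing below touches that model.

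**2. Inputs for the dose model.**
- N = 210, 1:1 (Protocol section 17.1). LOCF, with baseline carried forward where needed, keeps all randomised subjects in the analysis.
- Parameters now: intercept 1, treatment 1, four-level pre-trial treatment 3, covariates 2. Total 7, so 203 residual df, or 202 with weight added.
- r, the partial correlation of baseline weight with week-26 dose given the existing covariates: not in the documents. Assumed range 0 to 0.4.
- Residual SD of dose: not in the documents. Assumed 8 to 12 units.

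**3. Effect of adding weight.**

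Width factor = √[(1 − r²) × 203/202] × t(0.975; 202) / t(0.975; 203)

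Half-width = t × SD × √(2/105)

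| r | Width factor | Change | Half-width, SD 8 | SD 10 | SD 12 |
|---|---|---|---|---|---|
| weight not in model | 1 | – | 2.18 | 2.72 | 3.27 |
| 0 | 1.0025 | +0.25% | 2.18 | 2.73 | 3.27 |
| 0.1 | 0.9975 | -0.25% | 2.17 | 2.71 | 3.26 |
| 0.2 | 0.9822 | -1.8% | 2.14 | 2.67 | 3.21 |
| 0.3 | 0.9563 | -4.4% | 2.08 | 2.60 | 3.12 |
| 0.4 | 0.9188 | -8.1% | 2.00 | 2.50 | 3.00 |

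Half-widths are in units of insulin. The residual variance estimate falls once r² exceeds 1/203, that is r above about 0.07.

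**4. Effect of the 50-unit cap.** The formula takes r as given, but a cap flattens the relation between weight and dose. In simulated trials of 210 (assumed slopes of 0, 2 and 4 units per SD of weight, residual SD 10 units before the cap, weight/baseline-dose correlation 0.3 or 0.6, 11% to 49% of subjects at the cap), the ratio of standard errors with and without weight ran from 1.003 to 0.941. At the largest slope and correlation 0.3, it moved from 0.941 with 14% at the cap to 0.958 with 48% at the cap. With correlation 0.6 the corresponding values were 0.954 and 0.968. So the gain shrinks with more capping and with more overlap between weight and baseline dose.

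**5. Chance imbalance in weight.** Assume weight SD 12 kg, slope 0.3 units/kg and residual SD 12 units. The SE of the between-arm difference in mean weight is 12 × √(2/105) = 1.66 kg, which contributes 0.3 × 1.66 = 0.50 units. The residual SE is 12 × √(2/105) = 1.66 units. Combined: √(1.66² + 0.50²) = 1.73 units. The ratio 1.66/1.73 = 0.96 is the gain from adjustment itself. The unadjusted interval already allows for the imbalance, so counting it separately would count the same variance twice.

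**The case against.** The strongest reply is that nothing here is an error. Protocol and SAP specify the same model, randomisation makes it valid, and one more plausible covariate could be proposed for almost any ANCOVA in the plan. That stands.

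The textual support is also limited. Criterion 6 concerns BMI at entry, not kilograms among enrolled subjects, and half of its rationale is about weight loss. Protocol section 6.5 credits exploration of the higher dose range to enrolling insulin-treated subjects who need more treatment, and gives the BMI floor only the weight-loss reason. So the documents make weight a plausible predictor and do not show that it is one. This too stands.

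The pre-trial dose spans a 2.5-fold range and may already carry much of the body-size information. Doses carried forward from early withdrawals could weaken any relation further. Both would hold r down, which is why the range includes zero.

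The objection does not remove the balance of gain and cost. If weight adds nothing, the interval widens by about 0.25%. If it adds even modestly, the gain exceeds that.

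**Conclusion.** The point holds as a small efficiency improvement on a supportive endpoint. The dose model omits a baseline variable that the trial already holds and uses elsewhere, and including it would likely narrow the interval somewhat: about 1.8% at a partial correlation of 0.2, 4.4% at 0.3 and 8% at 0.4, less where many subjects sit at the cap, and nothing if the correlation is near zero. The partial correlation and the dose SD are assumptions.

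A reader might infer more than the documents support:
- **That the planned comparison is biased.** It is not. Randomisation protects it with or without weight.
- **That a loss of precision has been shown.** No slope or correlation is given, so a loss is likely but not established.
- **That chance imbalance in weight is a second harm.** It is the same variance, already inside the standard error.
- **That the trial's main claim is affected.** Dose is not a key endpoint and has no power target, and the HbA1c analysis and its 84.5% power do not change.

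**What to change.** In SAP section 2.4.1.1, under the insulin dose analysis, add baseline body weight (kg) as a covariate alongside baseline HbA1c and "baseline insulin dose as covariates". Take the value by the plan's own baseline rule: V2 if available, otherwise screening. Fix this before unblinding.

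The cost is one degree of freedom (203 to 202) and an interval about 0.25% wider if weight proves unrelated to dose. No new data, visits or other analyses are needed.
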